7.2.2. Subject ID Assignment

Subjects will be assigned a unique identification code (Subject ID). The subject ID is unique across all sites. After the subject is enrolled in the study, all forms will refer to the subject with the Subject ID and not the subject's name. Each site will maintain an Enrollment Log linking identity of study subjects to the Subject IDs.

7.2.3. Baseline Assessment

The Enrollment CRF captures Baseline assessment measures. These include:

- Date of birth/age
- Gender
- CTS severity (mild, moderate, or severe, from NCS)
- CTS diagnosis by hand (unilateral/bilateral, right/left/both)
- BCTQ and NPRS for affected hand(s)

7.2.4. Randomization

There are two treatment groups: active study device or sham device. Subjects will be equally randomized across all sites to ensure equal and equivalent active device and

sham groups. Randomization will occur using a Sponsor-supplied randomization tool or using the randomization module of the Electronic Data Capture (EDC) platform.

7.3. Treatment Period

The Treatment Period begins the first day that the subject begins wearing the device. Electronic Diaries are sent to subjects every day from the first day of treatment for 56 days. Subjects should be reminded if (s)he does not complete an entry. If 3 or more consecutive diary entries are missed, the site should contact the subject to remind them to complete entries or they could be withdrawn from the study. No more than 3 consecutive Diary entries and no more than 25% of total entries should be missed (14 out of 56 diary entries), but withdrawal due to missed Diary entries will be up to Sponsor after evaluating the situation

Follow-up surveys are electronically sent to subjects every 2 weeks from the subject's first day of device wear up to 8 weeks. The subject should complete the surveys within 3 days and reminders should be sent if the subject does not complete the survey. If the subject does not complete the survey within 3 days, the site should follow up with the subject to remind them to complete the survey and address any issues preventing the subject from completing the survey. All subject correspondences and contact attempts should be documented.

On the last day of treatment, the subject will complete a User Feedback Survey. This should be completed within 5 days.

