Demonstrate high subject compliance.	Diary wear time responses. Number of dropouts due to non-compliance.	Compliance is measured by adherence to daily wear and actual vs advised wear time.
Obtain user feedback on the comfort, use, and design of the study device.	User Feedback Survey responses at the end of Treatment Period	Collects qualitative data on practical aspects of the device.

5. Study Design

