5.2. Scientific Rationale

The study device was used in a pilot clinical trial (PPS-CTMD-15-001, ClinicalTrials.gov ID NCT02534493) that finished in October 2016 with promising results. Participants showed an average improvement in symptom severity scale (SSS) score of the Boston Carpal Tunnel Questionnaire (BCTQ) of 0.59 ± 0.68 points at 4 weeks (end of treatment period) compared to baseline SSS scores. After the 4-week treatment period, symptoms continued to improve for a total of 0.79 ± 0.74 points lower SSS compared to Baseline at 12 weeks.⁹ These results motivate the primary objective of this study.

The pilot study investigated the effects of the study device up to 4 weeks, but the trajectory of SSS did not indicate that improvement plateaued by 4 weeks. Thus, the treatment period is extended to 8 weeks in this study to determine if improvements continue with longer-term wear.

Analysis of the unilateral vs bilateral CTS patients showed a stark contrast in response. SSS of the unilateral patients improved 0.9 ± 0.5 points at 4 weeks and up to 1.2 ± 0.5 points at 12 weeks. In contrast, the bilateral patients appeared to show no improvement; however, the pilot study was not powered to detect differences in unilateral and bilateral subgroups. This difference is being explored as an exploratory objective in this study.

Most participants described the study device as being very comfortable and easy to wear. However, there were occasional comments about discomfort from the edges of the device. In Aim 1 of the NIBIB grant R44 EB024713-01, a series of experiments were conducted to investigate the applied pressures on wrists using tactile pressure sensors, the changes in median nerve dimensions using magnetic resonance imaging (MRI), and the changes in carpal tunnel or median nerve compression pressures in cadavers when the study device was applied to the wrist. This allowed the study device to be re-designed to fit a wider range of people and to reduce uncomfortable pressure points. A user feedback survey is incorporated in the present study to improve user satisfaction, which is critical for any practical application and success.

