7.5. Post-Treatment Period (Sham Device Group)

After the 56th day of treatment (end of Week 8), subjects will stop wearing the device. A post-treatment follow-up will then occur 4 weeks after the last day of treatment (Week 12). The sham group will be offered the active study device at this point. If the subject agrees, then (s)he will wear the active study device daily for an additional 8 weeks and complete Follow-up Surveys biweekly and Diary entries daily. On the last day of treatment (Week 20), the subject will complete a User Feedback Survey.

If the subject decides not to test of the active study device, then the subject will be Exited from the study.

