7.6. Exit Procedures

Exit procedures will only occur after the assigned site has ensured the subject has completed all required assessments and follow-ups. The assigned site staff member will complete the Exit CRF.

An Exit CRF must be completed for any subject that has signed the ICF and is being withdrawn for any reason.

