10.2. Sample Size Determination

A total of 102 subjects are required for this study, with 51 in each group.

The outcome measure used for calculations in the SSS of the BCTQ, which ranges from 1 to 5 with 1 being no symptoms (improved) and 5 being the worst symptoms (worsened).

A moderate effect size of 0.4 was chosen, assuming that study device efficacy is 0.4 greater than sham.

The pilot study experienced a drop-out rate of 20% (2 out of 13 total). With the longer treatment and follow-up times of this study, a higher drop-out is expected. Therefore the sample size calculation is modified by an estimated attrition rate of 25%.

The primary objective examines the 8 week vs baseline within-active group SSS change. Sample size determination explanation. The power analysis using the above results in a significance level of 0.05 and a power of 0.94*.

The secondary objective examines the change in SSS after 8 weeks between the active study device and sham groups. Sample size calculation is based on a parallel, one-sided t-test power analysis to identify an effect size of 0.4, standard deviation of 0.7 (based on the pilot study PPS-CTMD-15-001), significance level of 0.05, power of 0.8, and an estimated attrition rate of 25%.

The sample size was chosen to meet both the primary and secondary objectives.

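### The User Feedback Survey is scheduled only at the end of a completed 8-week wear period, so subjects who stop the device early are not asked about its comfort, use and design

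*Combined protocol and SAP*

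**What the plan says.** The last exploratory objective in Section 4 is: "Obtain user feedback on the comfort, use, and design of the study device". Its endpoint is "User Feedback Survey responses at the end of Treatment Period", and the explanation beside it reads "Collects qualitative data on practical aspects of the device".

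Three places set the timing, and they agree:

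- Section 7.3, for the first treatment period in both arms: "On the last day of treatment, the subject will complete a User Feedback Survey", with five days allowed to complete it.
- Section 7.5, for sham subjects who go on to wear the active device: "On the last day of treatment (Week 20), the subject will complete a User Feedback Survey".
- The Schedule of Events (Section 2.2) marks the survey as required at Week 8 in both arms. The sham table marks it again, as optional, at the end of the active-device period.

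For early withdrawal, Section 7.6 says: "An Exit CRF must be completed for any subject that has signed the ICF and is being withdrawn for any reason". Site staff complete that form, and Section 7.7 requires the reason for withdrawal to be recorded. Neither section mentions the User Feedback Survey. Section 10.5 says only that exploratory endpoints are analysed descriptively.

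**The concern.** The subjects best placed to say that the device is uncomfortable or impractical include those who gave it up. A survey tied to the end of a full wear period does not reach them.

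Comfort is not incidental here. Section 3.3.1 lists discomfort from the forces on the wrist as a device risk. Section 5.2 reports that in the pilot "there were occasional comments about discomfort from the edges of the device", and describes a redesign intended partly to relieve pressure points. The survey is the planned means of learning how users find the current design. If early stoppers are absent, the summary may look better than users' experience as a whole, and the sponsor may miss the comments most useful for further design work.

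**Working it through.** **1. What does the last day of treatment mean?** If it meant each subject's own last day of wear, early stoppers would be covered. The protocol's usage points the other way:

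- Sections 7.4 and 7.5 put the Week 12 follow-up four weeks after the last day of treatment, which makes that day Day 56.
- Section 7.5 equates the crossover subject's last day of treatment with Week 20.
- The Section 4 endpoint and the Schedule of Events tie the survey to the end of the period.

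Read together, these mean the scheduled end.

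**2. Does another instrument collect the same information?**

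- The Exit CRF (7.6, 7.7) is completed by staff and gives a reason for withdrawal. It is not described as collecting ratings of comfort, use or design.
- Diaries and surveys accept safety concerns (9.1), and adverse events that lead to stopping the device go to the sponsor (9.3). Section 9.2 limits adverse events to medical problems that were not expected, so mild, known discomfort may not be logged as one.
- Section 11.1 lists exit data among what surveys gather from subjects, without saying what those data contain.

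None of these is shown to replace the survey.

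**3. How many subjects could be missed?** Section 10.2 states: "Therefore the sample size calculation is modified by an estimated attrition rate of 25" per cent. Its inputs are a difference of 0.4, SD 0.7, one-sided alpha 0.05, power 0.8 and 51 per arm. Reproducing the plan's figure:

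- Evaluable n per arm = 2 × (1.645 + 0.842)² × (0.7/0.4)² ≈ 37.9, rounded up to 38.
- Enrolled n per arm = 38 / 0.75 = 50.7, rounded up to 51, which matches the plan.
- Planned loss = 51 − 38 = 13 per arm.

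Thirteen per arm is an upper guide. The 25% is attrition for any reason, and Section 10.2 attributes it to longer treatment and follow-up together. Anyone lost after Week 8 would already have been sent the survey.

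**4. How far could the summary shift?** Let d be the proportion lost, f the share of those who stopped for discomfort, and g the gap in the proportion calling the device comfortable (completers minus discomfort stoppers). Assume that other dropouts rate as completers do. If c is the completers' proportion:

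- All-subject proportion = (1 − d)c + d[f(c − g) + (1 − f)c] = c − dfg.
- Overstatement = d × f × g.

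Only d has any basis in the documents; f and g are assumptions.

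| d | f (assumed) | g (assumed) | Overstatement, percentage points |
|---|---|---|---|
| 0.25 | 0.10 | 0.2 | 0.5 |
| 0.25 | 0.25 | 0.5 | 3.1 |
| 0.25 | 1.00 | 0.5 | 12.5 |
| 0.25 | 1.00 | 1.0 | 25.0 (ceiling) |
| 2/13 = 0.154 (pilot count) | 1.00 | 1.0 | 15.4 (ceiling) |

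Section 10.2 labels the pilot's 2 of 13 as 20%; the table uses the count. A range from half a point to 25 points shows that the documents do not fix the size.

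**The case against.** The best defence is that this is an exploratory, qualitative objective with no score, threshold or test. Feedback after a full wear period is a reasonable basis for design comments. Section 5.2 says most pilot participants found the device very comfortable, and complaints were occasional. Stopping for discomfort would still show through diaries, adverse event reports and recorded withdrawal reasons. The survey instruments are separate documents, so the exit or follow-up forms might ask about comfort. Many subjects lost to follow-up would not answer an extra survey anyway.

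Most of this stands as a limit on importance. It does not close the gap, because no text in the plan obtains the same feedback from an early stopper.

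Three stronger readings are tempting, and the documents do not support them:

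- **That comfort will be overstated by a known amount.** The direction is plausible, but no rate of stopping for discomfort is given. The 25% is overall attrition, not device stopping.
- **That sham ratings of a cushioned device contaminate the result.** Both arms answer at Week 8, but nothing says their answers will be pooled. Using one survey in both arms is consistent with the blind, and allocation is known at analysis. The cushion's effect on comfort is undocumented. What is missing is only a statement that results are summarised by device.
- **That early discomfort goes wholly unrecorded.** The other reporting routes exist, although they are not comfort ratings.

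**Conclusion.** The point holds as a minor design gap. As written, the survey is given only to subjects who reach the end of a treatment period, and no early-stopping trigger exists. The resulting feedback is likely, but not certain, to favour the device. Its size cannot be estimated; about 13 of 51 per arm is an upper guide to the number missed.

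This rests on two assumptions: that the last day of treatment means the scheduled day, and that the unseen forms do not already ask early stoppers the same questions. The plan also does not say whether a subject who stops wearing the device but stays in follow-up is sent the Week 8 survey; any who are would not be missed.

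No efficacy endpoint, alpha, power or sample size is affected.

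**What to change.** In Sections 7.3, 7.5 and 7.6 and the Schedule of Events, keep the Week 8 and Week 20 surveys. Add that the same survey is sent at permanent discontinuation of the device or at exit during a treatment period, whichever comes first. Align the endpoint wording in Section 4.

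In Section 10.5, state that responses are summarised by device worn, with early stoppers shown alongside completers. Also report how many early stoppers did not respond, with their documented reasons for stopping.

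The cost is one more trigger for an existing electronic survey and a few lines of text. Some early stoppers will not answer, so the selection is reduced rather than removed; the count of non-responders lets a reader judge what remains.

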7.4. Post-Treatment Period (Active Study Device Group)

After the 56th day of treatment (end of Week 8), subjects will stop wearing the device. A post-treatment follow-up will then occur 4 weeks after the last day of treatment (Week 12). Survey completion and reminder timelines are the same as for the Treatment Period Follow-up Surveys above.

Subjects in the treatment group will be exited after the last day of the Post-Treatment Period (end of Week 12) and after they have completed all required surveys and follow-ups. See [Section 7.6 Exit Procedures](#).

7.5. Post-Treatment Period (Sham Device Group)

After the 56th day of treatment (end of Week 8), subjects will stop wearing the device. A post-treatment follow-up will then occur 4 weeks after the last day of treatment (Week 12). The sham group will be offered the active study device at this point. If the subject agrees, then (s)he will wear the active study device daily for an additional 8 weeks and complete Follow-up Surveys biweekly and Diary entries daily. On the last day of treatment (Week 20), the subject will complete a User Feedback Survey.

If the subject decides not to test of the active study device, then the subject will be Exited from the study.

7.6. Exit Procedures

Exit procedures will only occur after the assigned site has ensured the subject has completed all required assessments and follow-ups. The assigned site staff member will complete the Exit CRF.

An Exit CRF must be completed for any subject that has signed the ICF and is being withdrawn for any reason.

7.7. Subject Withdrawal

Potential reasons for withdrawal or removal of subjects are outlined below:

- Subject decides it is in his/her best interest to withdraw
- Principal investigator decides it is in the subject's best interest to withdraw
- Subject is noncompliant during the 12-week treatment period (i.e., Sponsor deems subject has missed too many Diary entries or Follow-ups).
- Subject is lost-to-follow-up at any point (more than 5 documented attempts to contact and ask to complete follow-ups with no response after 3 weeks)
- Subject fails to refrain from other CTS treatments or therapies.

If the subject is withdrawn, the PI or designated staff member must fill out the Exit Form and document the reason for withdrawal or removal of the subject from the study. Unless the subject requests removal of their data, any data or information collected from the subject will remain in the database and analyzed at the sponsor's discretion.

8. Study Supplies

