9.4. Follow-up for Adverse Events

Site staff should contact subjects that report an AE within 3 days of learning of the AE, unless the AE is minor (see above).

For subjects with a reported and recorded AE, site staff should contact the subject at each subsequent Follow-up (i.e., every 2 weeks during Treatment Period, every 4 weeks during Post-Treatment Period) to obtain an update on the status of the AE/SAE. The AEs should be followed until resolved, considered stable, or the subject is exited from the study.

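### Subjects who use another CTS therapy or miss diaries may be withdrawn from the study, and no pathway keeps collecting their BCTQ or clearly continues AE follow-up

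*Combined protocol and SAP*

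**What the plan says.** Section 7.7 opens with "Potential reasons for withdrawal or removal of subjects are outlined below". Two of the reasons listed matter here: "Subject fails to refrain from other CTS treatments or therapies" and "Subject is noncompliant during the 12-week treatment period (i.e., Sponsor deems subject has missed too many Diary entries or Follow-ups". The section then calls for an Exit Form. Data already collected stay in the database, to be analysed as the Sponsor sees fit; later collection is not mentioned.

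Section 7.3 confirms that the consequence of missed diaries is leaving the study: after three or more consecutive missed entries the site should "contact the subject to remind them to complete entries or they could be withdrawn from the study". It gives limits for missed entries (3 consecutive, 14 of 56 in total), but adds that "withdrawal due to missed Diary entries will be up to Sponsor after evaluating the situation".

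Section 7.6 makes exit conditional on completion of the required assessments. Its next paragraph says "An Exit CRF must be completed for any subject that has signed the ICF and is being withdrawn for any reason". Section 9.4 says "The AEs should be followed until resolved, considered stable, or the subject is exited from the study".

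Section 6.3 bars other CTS therapies for the whole study, which includes Weeks 8 to 12, when neither arm wears a device (7.4, 7.5). Section 4 makes the Week 12 between-group SSS comparison a secondary endpoint. Section 10.4 limits the analyses to subjects who completed the 8-week treatment period.

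**The concern.** The BCTQ is completed online at home, so a subject who returns to a splint or stops filling in diaries can still answer it. The plan nevertheless offers only one status change, from in the study to out of it. Two kinds of SSS value can be lost as a result:

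- Week 8, for a subject withdrawn before the end of treatment.
- Week 12, for a subject who completed 8 weeks, belongs to the Section 10.4 population, and starts another therapy in Weeks 8 to 12.

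People who seek other treatment are plausibly those whose symptoms persist or return. That is an inference, not a statement in the documents. If it holds, the missing values are related to outcome. The within-active Week 8 improvement would then look larger than it is, and the Week 12 result more sustained. The between-arm difference could be biased in either direction, depending on which arm loses more such subjects. No later choice of analysis set can recover values that were never collected.

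On safety, withdrawal while an AE is unresolved would, on the wording of 9.4, end its follow-up.

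**Working it through.** **1. The plan's own figure.** Inputs from Section 10.2: difference 0.4, SD 0.7, one-sided alpha 0.05, power 0.8, attrition 25%.

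n per arm = 2 × (0.7/0.4)² × (1.645 + 0.842)² = 37.9, so 38. With attrition, 38/0.75 = 50.7, so 51 per arm and 102 in total. This matches the plan, which therefore expects to lose about 51 − 38 = 13 subjects per arm from all causes.

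**2. Is there an off-protocol but still-followed pathway?**

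- 7.3 and 7.7: withdrawal is from the study.
- 7.7: earlier data are kept; nothing is said about later data.
- 7.6: the first sentence would hold exit back until follow-ups are complete, but the following one provides an Exit CRF for subjects withdrawn for any reason. It does not clearly require surveys after withdrawal.
- 9.4: exit ends AE follow-up.
- 2.2: the surveys are scheduled by week, with no row for withdrawn subjects.

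No such pathway is described.

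**3. Size of the effect on those left.** Assumptions: SD of change 0.7 (10.2); correlation rho of 0.3 to 0.5 between the tendency to stay and improvement, which is not in the documents. If a fraction p is lost, mean improvement among those left rises by

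SD × rho × phi(z_p)/(1 − p),

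where phi is the standard normal density and z_p the cut-off for a fraction p.

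| p | phi(z_p)/(1 − p) | rho 0.3 | rho 0.5 |
|---|---|---|---|
| 10% | 0.1755/0.90 = 0.195 | 0.7 × 0.3 × 0.195 = 0.04 | 0.7 × 0.5 × 0.195 = 0.07 |
| 25% | 0.3178/0.75 = 0.424 | 0.7 × 0.3 × 0.424 = 0.09 | 0.7 × 0.5 × 0.424 = 0.15 |

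The 25% row is an upper bound, because planned attrition also includes subjects who cannot be reached or who withdraw consent.

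**4. A cruder cross-check.** Suppose those left improve by 0.40 and those lost do not change. The mean over everyone is then 0.90 × 0.40 = 0.36 with 10% lost, and 0.75 × 0.40 = 0.30 with 25% lost: overstatements of 0.04 and 0.10, of the same order as step 3.

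**5. Between arms.** If sham loses 25% and active 10% in this way (assumed), the difference shrinks by 0.148 − 0.068 = 0.08 at rho 0.5, or 0.089 − 0.041 = 0.05 at rho 0.3. If the rates are reversed, it grows by the same amounts in favour of the device.

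**The case against.** Several stronger readings are tempting, and the documents do not support them.

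- *Removal is automatic.* It is not. The reasons in 7.7 are potential ones, and 7.3 requires a site reminder first and leaves the diary decision to the Sponsor. This stands, though discretion does not supply the missing pathway. The Sponsor's Clinical Research Manager can also see subject responses (9.3, 11.2), so removals may be decided with outcomes visible, even with allocation blinded.
- *Stopping the device, or a skin reaction, leads to exit.* Neither is a listed reason. Section 9.3 treats an AE that ends device use as reportable, and 9.4 has staff contact the subject at each later follow-up. Only a separate withdrawal would close that. AEs recorded before exit still count, because the safety analysis covers all treated subjects (10.5).
- *Relapse in Weeks 8 to 12 costs the Week 8 value.* It does not; 7.7 keeps data already given. Only Week 12 is at risk.
- *Continued surveys would raise power.* A reader might reason that recovering about half of the 13 losses takes each arm from 38 to 44 and power from 0.795 to 0.845. Under 10.4, subjects who stop before Week 8 stay out of the planned tests even if they keep answering, so this gain is not available.
- *Subjects with missed diaries are failing.* Nothing in the documents links the two.

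It is also fair to object that the correlation and the unequal loss rates are assumed, and that the planned 25% is not broken down by cause. The flow-chart in Section 2.3 and the content of the exit data mentioned in 11.1 were not available for this check and could clarify the intent.

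**Conclusion.** The point holds in a limited form. The plan permits study withdrawal for other CTS therapy or for missed diaries and follow-ups. It describes no BCTQ collection afterwards, and it ends AE follow-up at exit. Outcome-related SSS data that are cheap to collect can therefore be lost.

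Under the stated assumptions the distortion of mean improvement is 0.04 to 0.07 points for 10% outcome-related loss and at most 0.09 to 0.15 for 25%, against a target of 0.4. The sign of the between-arm bias is unknown. The clearest gain within the plan as written is at Week 12, for 8-week completers who start another therapy. For early stoppers the gain is a sensitivity analysis only.

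Two wording conflicts need reconciling. Sections 7.6, 7.7 and 9.4 do not agree on what withdrawal means for follow-up. Section 7.7 also gives the treatment period as 12 weeks where 5.1, 7.3, 7.4 and 7.5 give 8; the effect of this on the data is small, since withdrawal after a missed Week 12 survey removes no earlier value.

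**What to change.** - In 7.7, separate stopping the device, or breaking the therapy or diary rules, from withdrawing from the study. For the other-therapy and missed-diary reasons, keep sending the scheduled online BCTQ surveys through Week 12 unless the subject withdraws consent, cannot be reached, or is withdrawn by the investigator in the subject's best interest.
- Record the date device wear stopped, and the date and type of any other CTS therapy.
- In 10.5, add a sensitivity analysis of all randomised subjects with a Week 8 SSS, including early stoppers. Claim no power gain for the planned tests.
- Reconcile 7.6, 7.7 and 9.4 on whether withdrawal ends follow-up of an unresolved AE, and reconcile the 12-week treatment period in 7.7 with the 8 weeks stated elsewhere.

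None of this alters which therapies are allowed or when a subject stops the device. The cost is protocol wording, more reminders on surveys that are already electronic, and some SSS values recorded off device or on another therapy, which must be flagged.
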